***Full Study Title: Napping, Sleep, Cognitive Decline and Risk of Alzheimer's Disease***

Principal Investigator: [name]

University of California, San Francisco  
[name]  
[name]  
[contact]

Sponsor

National Institutes of Health

Title	Napping, Sleep, Cognitive Decline and Risk of Alzheimer's Disease (SleepTIGHT)
Study Duration	Trial duration: 9 weeks + follow-up after 24 weeks
Study Center	UCSF Psychiatry department
Objective	Determine feasibility of online CBT-I in an older adult population (age 65+)
Number of Subjects	40
Diagnosis and Main Inclusion Criteria	
Inclusion Criteria
 
 
• 1) Age 65+,
 
• 2) evidence of MCI, defined as: self-reported quick dementia rating system (QDRS) - derived global clinical dementia rating score of .5,
 
• 3) adequate visual and auditory acuity to allow neuropsychological testing;
 
• 4) evidence of subthreshold or clinical insomnia, defined as a score of 8 or more on the insomnia severity index,
 
• 5) ability to speak understand and write in English, 6) study partner willing to participate,
 
• 7) capacity to give written informed consent; and
 
• 8) owns one or more smartphone or tablet devices that can be used to access the internet and to participate in video conferences.
 
 
Exclusion Criteria
 
 
• 1) Self-reported diagnosis by a physician of any major neurologic disease such as Alzheimer's disease, other dementia, Parkinson's disease, multiple sclerosis, epilepsy, Huntington's disease;
 
• 2) History of brain tumor or significant head trauma (loss of consciousness >30 minutes);
 
• 3) Evidence (CT or MRI scans within 12 months prior to screening) of brain infarction or other focal lesions; 4) Any comorbid psychiatric conditions or severe personality disorder within the past 2 years (by DSM-V), such as major depression, bipolar disorder, schizophrenia, and other psychotic features;
 
• 5) Any uncontrolled medical conditions or systemic illness that might lead to difficulty complying with the study protocol;
 
• 6) Any concomitant treatment that might confound the results (participants must be off all psychotropic medications, including hypnotic medications, and non-pharmacological treatments, for at least 30 days prior to screening);
 
• 7) History of alcohol or substance abuse within the past 2 years;
 
• 8) Shift workers; and
 
• 9) Any inadequately treated primary or secondary sleep disorders
 

### Purpose

In order to address the hypothesis that CBT-I is feasible in patients with MCI, and could potentially improve their sleep quality, slow down cognitive decline, and improve quality of life of patients and caregivers, we will use a parallel-designed randomized controlled trial to pilot test the feasibility and effects of a digital CBT-I treatment program in those with MCI.

This study focuses on testing the validity of this CBT-I program while exploring its preliminary effects on sleep/cognition.

### Duration of the Study

Screening + Intervention + post-study screening: 10 – 13 weeks

Post-treatment follow-up: After 24 weeks

### Setting

The trial will take place remotely, with all activities and assessments done over phone or Zoom video call or app on smart device.

### Description of the Intervention

We will randomize patients, using computer-generated random numbers, to one of two treatment arms:

- a) an FDA-authorized prescription digital CBT-I therapeutic treatment
- or
- b) an interactive, attention-matched, internet-based placebo control program.

At the beginning of the intervention, study staff will give instructions on the use of the programs via zoom.

Throughout the intervention, study staff will call the participants weekly to give further clarifications and answer questions. Somryst is a 9-week program that delivers digital CBT-I therapeutic content, and can be used on a mobile device, such as a smartphone or tablet. CBT-I is a neurobehavioral treatment which focuses on addressing the maladaptive behaviors, routines, and dysfunctional thoughts that perpetuate sleep problems, regardless of the cause of sleep problems. CBT-I can be conceptualized as six sessions or cores that deliver proven behavioral and cognitive treatment strategies.

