**Guidelines for Scoring/Interpretation:**

Add the scores for all seven items (questions 1 + 2 + 3 + 4 + 5 + 6 + 7) = \_\_\_\_\_ your total score

Total score categories:

0–7 = No clinically significant insomnia

8–14 = Subthreshold insomnia

15–21 = Clinical insomnia (moderate severity) 22–28 = Clinical insomnia (severe)

**Informed Consent Review** [either continuation of above telephone conversation or in later call]

Note: the Informed Consent does not have to be read word-for-word over the telephone but major points need to be reviewed, including:

- Subject Bill of Rights
- Background and Purpose
- Study Procedures/Plan
- Responsibilities
- Potential Benefits
- Confidentiality
- Participation is Voluntary
- Medical Treatment and Compensation
- Significant New Information
- Time Requirements
- Possible Risks and Discomforts
- Alternatives to Participate
- Costs and payments
- Right of Investigator to Withdraw Subjects

Persons to Contact if Questions:

Contact Information: [name] at [contact]

For questions about your rights as a research participant, you can call the UCSF Institutional Review Board at [contact].

- Would you be interested in being screened to see if you're eligible for this research? It will take about 30 minutes to go over these questions.
- It's fine if you want to get back to us later about scheduling a telephone screening appointment.  [If potential subject wants to schedule phone appointment] When would be a good day and time?

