3 Follow-up and outcome measures. The primary goal of this research is to pilot test the feasibility of implementing this CBT-I program in patients with MCI or mild AD. Following the last session of CBT-I, participants will be asked to report their satisfaction and acceptability of the treatment. We will also assess eligibility, consent, and retention rates, as well as data quality and completeness. To explore the initial effects of this treatment on sleep and cognition, we will repeat baseline measurements, including the neuropsychological battery and the questionnaires (ISI, PSQI, ESS and SF-36) towards the end of the intervention.

STATISTICAL ANALYSES

To assess the randomization, baseline demographic and clinical characteristics will be compared between arms using parametric (e.g. t-test) or nonparametric test (e.g. chi-square, Wilcoxon tests); variables that are not balanced across treatment arms will be adjusted for in subsequent analyses. The primary analysis will use the intent-to-treat principle. Secondary subgroup analyses will assess the role of treatment adherence on outcomes, using measures of compliance applicable to both study arms, thus avoiding the well-known biases of a “compliers only” analysis.

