For Aim 2 and the Exploratory Aim, we will use t-tests, Wilcoxon or chi-square tests to compare between the treatment and non-treatment groups the change scores in: 1) circadian rhythms parameters (e.g. amplitude, and overall rhythmicity); 2) frequency and length of day naps; 3) quality of nocturnal sleep (e.g. change in ISI scores; increased sleep duration and efficiency; decreased sleep onset time); 4) reported quality of life (SF-36 scores); 5) cognitive scores. Standardized measures of cognitive performance (z-scores) will be calculated for each participant for each neuropsychological test in the battery. Repeated measures models will be used to examine longitudinal treatment effects. These models will include subject-specific (i.e. intercept term) and fixed effects (treatment group, time and the time*treatment interaction). A significant time*treatment interaction will indicate that changes in outcome measures over time are different in the treatment arms. In order to explore the impact of involvement of caregivers, we will repeat the above analysis between the treatment group with and without involvement of the caregiver. The resulting estimates will be imprecise, and thus useful for trial planning only in combination with external data, expert opinion, and established norms for clinically meaningful effects.

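### The SAP picks covariates by testing baseline differences and otherwise compares unadjusted change scores; fixing baseline adjustment in advance would recover precision for Aim 2 and the exploratory outcomes at almost no cost

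*Protocol*

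**What the plan says.** The protocol synopsis gives the trial size: "Number of Subjects 40". Entry requires "a score of 8 or more on the insomnia severity index" with no upper limit, so baseline severity can run from the band labelled "8–14 = Subthreshold insomnia" in the protocol's ISI scoring guide up to severe clinical insomnia.

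The SAP's Statistical Analyses section sets the covariate rule in two steps. First: "To assess the randomization, baseline demographic and clinical characteristics will be compared between arms", by t-test, chi-square or Wilcoxon test. Second: "variables that are not balanced across treatment arms will be adjusted for in subsequent analyses". It gives no significance level, no list of variables and no covariate fixed in advance.

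For Aim 2 and the Exploratory Aim the SAP states: "we will use t-tests, Wilcoxon or chi-square tests to compare between the treatment and non-treatment groups the change scores in" five groups of outcomes, with change in ISI named as an example under nocturnal sleep. The repeated measures models contain a subject-specific intercept and "fixed effects (treatment group, time and the time*treatment interaction"). Neither analysis lists a baseline value as a covariate.

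On allocation, the protocol (Description of the Intervention) and the SAP (Procedures, item 2) share one sentence: "We will randomize patients, using computer-generated random numbers, to one of two treatment arms". Nothing in the available text adds a ratio, blocks, strata or concealment.

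**The concern.** After randomisation, any baseline difference is due to chance, so a significance test says little about whether a covariate matters. What matters is how strongly the covariate predicts the outcome. A test-then-adjust rule goes wrong in two directions. It misses moderate imbalances in strongly related variables, because 40 participants give the test little power. It also brings in unrelated variables that happen to cross the threshold. The final model therefore depends on the data and cannot be written down beforehand.

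Where the rule flags nothing, the change-score comparison is what remains. It uses the baseline value with a fixed coefficient of one, whereas the best coefficient is the regression slope of follow-up on baseline, usually below one. The arm that starts worse by chance will then tend to show more improvement through regression to the mean.

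At stake is the precision of the sleep, quality-of-life and cognition estimates, which the SAP wants for planning a later trial.

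**Working it through.** **Inputs from the documents.** N = 40; two arms; no alpha, SD, effect size, correlation, ratio or number of baseline tests. There is therefore no stated figure to reproduce.

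**Assumptions.** 1:1 allocation; baseline tests at two-sided 0.05; ISI in SD units with equal SD at both visits; baseline-to-follow-up correlation ρ of 0.3, 0.5 or 0.7; true effect 0 or 0.7 SD; full follow-up.

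**1. What the baseline test can see.** At 20:20 the standard error of a baseline difference is √(1/20 + 1/20) = 0.316 SD. The smallest difference flagged is t(0.975, 38 df) × 0.316 = 0.64 SD.

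**2. How often a sizeable imbalance is missed.** By normal approximation, P(|difference| > 0.5 SD) = 11.4% and P(> 0.25 SD) = 43%. About 5% of trials are flagged, all with larger differences. That leaves 11.4 − 5 ≈ 6% of trials above 0.5 SD, and 43 − 5 ≈ 38% above 0.25 SD, treated as balanced.

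**3. What a missed imbalance does to a change score.** Given a chance baseline difference d, the expected error of the change-score contrast is −(1 − ρ)d. For d = 0.5 SD this is 0.35, 0.25 and 0.15 SD in size at ρ = 0.3, 0.5 and 0.7. Under a linear model, adjusting for baseline removes it.

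**4. False flags.** With m independent tests, P(at least one flagged by chance) = 1 − 0.95^m: 23% for 5, 40% for 10 and 64% for 20.

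**5. Cost in precision.** The variance of a change score is proportional to 2(1 − ρ), and that of ANCOVA to 1 − ρ². The ratio of ANCOVA to change score is (1 + ρ)/2, or 0.65, 0.75 and 0.85, before ANCOVA's small penalty for estimating the slope.

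Simulation under unrestricted 1:1 allocation (4,000 trials per setting) compared the SAP rule, taken as a change score unless the baseline of the outcome itself is flagged and ANCOVA if it is, with ANCOVA in every trial. A second set of simulated trials accounts for the power ranges; simulation error is about 1 point.

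| ρ | SE, SAP rule | SE, ANCOVA | Power, SAP rule | Power, ANCOVA | Type I error, SAP rule |
|---|---|---|---|---|---|
| 0.3 | 0.358 | 0.307 | 44% | 59–60% | 4.2% |
| 0.5 | 0.311 | 0.285 | 57% | 66–67% | 4.3% |
| 0.7 | 0.248 | 0.235 | 79% | 83–84% | 4.9% |

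**6. The allocation question, if allocation is unrestricted.** From the Binomial(40, 0.5), P(24:16 or worse) = 26.8% and P(26:14 or worse) = 8.1%. Information lost is 1 − 4ab/40²: 1 − 4·24·16/1600 = 4% and 1 − 4·26·14/1600 = 9%. Blocks of 4 within two severity strata cut P(baseline difference > 0.5 SD) from about 12% to about 1%. With ANCOVA already in place, however, such blocks lower the standard error only from 0.310 to 0.303, 0.280 to 0.273 and 0.232 to 0.227 at the three correlations, about 2%.

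**The case against.** The strongest reply is that this is a pilot with feasibility and acceptability as its primary outcomes. The proportions consented and randomised are settled before or at allocation, so no choice of covariates can alter them. The SAP also concedes that its effect estimates will be imprecise and of use only alongside outside evidence. All of this stands, and it limits the importance of the point. It does not defend the rule: imprecision from 40 participants is unavoidable, but the part described here is not.

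Second, baseline severity is not ignored. Change scores and the subject intercept with a time-by-treatment term both use the baseline value. This also stands, so it would be wrong to say that data-driven adjustment is the SAP's only handling of baseline. But with two visits and complete data the interaction estimates the same quantity as the change-score contrast, so it has the same weakness.

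Third, a reader might infer from the allocation sentence that the trial uses simple randomisation. The documents do not say so. The sentence names the source of the sequence, and a permuted-block list is computer-generated too. The study figure and some pages are also unavailable. Only the absence of a stated scheme is supportable; the probabilities in step 6 of the working are conditional on unrestricted allocation.

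Fourth, blocking and stratifying are not free. Study staff brief participants on their assigned program, so anyone who also enrols could guess the next assignment near the end of a small block.

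**Conclusion.** The point holds for the covariate rule. As written, the SAP leaves about 6% of trials with an unadjusted baseline ISI difference above 0.5 SD and lets the model depend on which tests happen to cross a threshold. Prespecified baseline adjustment would gain roughly 16, 10 and 4 points of power at assumed correlations of 0.3, 0.5 and 0.7 for an assumed 0.7 SD effect. The direction does not depend on those choices: with equal SDs, (1 + ρ)/2 is below one for any correlation short of perfect. The size does depend on them, and the documents supply none of the inputs.

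A reader might infer that the rule inflates false positives. Simulated type I error was 4.2% to 4.9%, so it does not. Nor do the documents show that ISI severity is the strongest predictor of every sleep outcome; the argument needs only that a baseline value is related to its own follow-up value.

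This is an inexpensive improvement to the secondary and exploratory analyses, not a defect in the primary objective. The missing allocation details are a reporting gap with little bearing on precision once baseline is in the model.

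**What to change.** **Main change, in the SAP's Statistical Analyses section.**
- Delete the rule that adjusts for variables found unbalanced. Keep the baseline table as description, without tests.
- Analyse each continuous outcome by ANCOVA on the follow-up value, or by a repeated measures model of the post-baseline visits, adjusted for that outcome's own baseline value.
- Name baseline ISI as a covariate for the other sleep outcomes as well.
- For skewed or count outcomes such as nap frequency, name a baseline-adjusted method in advance.

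This costs a few sentences and one or two degrees of freedom. The Schedule of Evaluations already collects ISI, questionnaires, actigraphy and cognition before treatment, so participants carry no extra burden. The change should be dated before outcomes are seen by arm; if that is no longer possible, report it as a post hoc analysis beside the original.

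**Secondary change, in both documents.** State the allocation ratio, whether the list is blocked or stratified, and how it is concealed. If allocation is in fact unrestricted and the list can still be altered (enrolment status is not given), concealed 1:1 permuted blocks of varying size, stratified by ISI 8–14 versus 15 or more, would limit imbalance. The stratum should then enter the models, or baseline ISI in its place. The expected gain is about 2% in standard error; the price is a new list and somewhat more predictable allocation in small blocks.

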### Potential Benefits and Risks to Participants

There will be no direct benefit to the participants from taking part in this study. Taking part in this study may or may not make their health better. While doctors hope that cognitive training therapies will be beneficial, these trainings are still being studied.

Some of the most likely risks of participation in this study include:

- Risk of fatigue/distress: Finding study activities difficult, tiring, time-consuming, anxiety-provoking, frustrating, or boring. Participants are free to decline to answer any questions or to stop at any time. To reduce fatigue, breaks are scheduled during testing and training sessions. Additional breaks will be provided at the participant's request. If the participant appears to be under undue strain, the session will be discontinued.
- Risk of loss of privacy: Participation in research may involve a loss of privacy. Because training takes place in a small group setting, other research subjects within the group may become aware of information that participants would prefer to not be shared outside of the group. Researchers will ask all subjects to keep private all information learned about other group members and to not talk about this information outside of group sessions. However, absolute confidentiality cannot be guaranteed. The researchers will keep information about participants as confidential as possible, but complete confidentiality cannot be guaranteed. On rare occasions, a court has subpoenaed research records. Other University of California personnel may also review or receive information about the participants. Study PI and research staff will retain the participant's research records indefinitely for research purposes. Personal identifiable information (PII) and protected health information (PHI) cannot be used for additional research without additional approval from either the participant or a review committee.
- Unknown risks: The experimental treatments may have risks or side effects that no one knows about yet. Members of the research team will inform participants about any new information that may impact their decision to remain in the study.

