### **Reasons for Participant Withdrawal or Termination**

Participants can decide to stop at any time. The study doctor may stop participants from taking part in this study at any time if the doctor believes it is in the participant's best interest, if the participant does not follow study rules, or if the study is stopped

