### If continued interest, eligible, and consented

- Schedule meeting for briefing via Zoom on Somryst program or placebo condition materials
- Intervention **or** attention-matched placebo program (6 weeks) + Weekly meetings with research team for clarification or assistance with materials and content

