## B. FOLLOW-UP MEASURES

Once intervention is completed,

- Feedback at the end of trial via survey and phone follow-up (if needed)
- Follow-up (3-day actigraphy & questionnaires + Cognitive Assessments)
- Follow-up at 24 weeks:
- Final follow-up actigraphy watch measurement
- Follow-up of cognitive assessment + questionnaires

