## Data Collection and Storage

Patient information is collected and stored in REDCap.

Once assessments are completed, they will be scored and recorded for later analysis.

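### In the text available, neither arm has discrete adverse events systematically asked about, recorded or tabulated; repeated scales cover some symptoms but are not an event record.

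*Protocol*

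**What the plan says.** The protocol's section on potential benefits and risks lists fatigue or distress, loss of privacy, and unknown risks, and states: "The experimental treatments may have risks or side effects that no one knows about yet". The actions attached are breaks, ending a session if the participant is under strain, and telling participants about new information. Under reasons for withdrawal, "The study doctor may stop participants from taking part in this study at any time", including when that is in the participant's best interest.

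There is regular contact. The description of the intervention says "study staff will call the participants weekly to give further clarifications and answer questions". The section for eligible and consented participants lists, for both the active and placebo programs, "Weekly meetings with research team for clarification or assistance with materials and content". Follow-up after the intervention consists of a feedback survey with a phone call if needed, actigraphy, questionnaires and cognitive tests, then a "Follow-up at 24 weeks" with the same kinds of measurement.

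On data, the protocol says "Patient information is collected and stored in REDCap" and that assessments are scored for later analysis. The SAP's follow-up section says "We will also assess eligibility, consent, and retention rates, as well as data quality and completeness". Its statistical section lists between-arm comparisons of change in circadian parameters, naps, nocturnal sleep, SF-36 and cognition.

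**The concern.** A participant could fall, have an accident, become low in mood or be admitted to hospital, and nothing in the visible plan would have staff ask about it or put it in an analysable field. Staff may well hear of such events on the weekly calls, but the stated purpose of those calls is help with the program, and no script or form makes asking or recording uniform.

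The population and treatment make this more than a formality. The Sleep Window core is sleep restriction. It is delivered by app, with all contact remote, to people aged 65 or over with cognitive impairment. The program is described as FDA-authorized, but the protocol's purpose is to pilot it in people with MCI.

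Events that nobody asks about cannot be reliably recovered at analysis. A later trial would then be planned without an event rate from this pilot, and the pilot could say little about whether the program was tolerated beyond what scales, withdrawals and acceptability feedback show.

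**Working it through.** The plan states no event rate, power or precision for harms, so there is no figure of its own to reproduce. The check has three parts.

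**1. Where event capture could appear**

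- Schedule of evaluations: eligibility, history, scales, actigraphy and cognition. No event row.
- Weekly contacts (protocol and SAP): clarification, questions and help with materials. No harms question.
- Follow-up measures: feedback survey, actigraphy, questionnaires, cognition. No event item.
- Primary outcomes: feasibility counts, then satisfaction, acceptability, barriers and burden, and an interview. No safety item. Burden and the interview come closest, but they serve acceptability.
- Data collection and storage: no event field.
- SAP follow-up and analyses: retention, data quality and change scores. No event count or table.

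**2. What the repeated measures cover**

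ISI, PSQI, Epworth, SF-36 and cognition are repeated at about week 9 in both arms, and actigraphy is repeated too. Sleepiness can therefore be compared on the Epworth, although the SAP's list of comparisons does not name that scale. SF-36 has mood items, so it gives partial cover there. The Geriatric Depression Scale is scheduled at baseline only. None of these measures records a fall, an accident or a serious event.

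After week 9 the next planned contact is the 24-week follow-up. Counted from the start of treatment (one reading of the synopsis), that leaves 24 − 9 = 15 weeks. Counted from the end of treatment ("Post-treatment follow-up: After 24 weeks"), it leaves 24 weeks. The intervention section describes six weeks of meetings, so the weekly contacts may stop before week 9.

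**3. What systematic asking would yield**

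Inputs: N = 40 and two arms (protocol). Assumption: 1:1 allocation, so 20 per arm; the ratio is not stated.

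- Zero events in n, one-sided 95% upper limit = 1 − 0.05^(1/n). For n = 20: 13.9%. If only 18 or 16 are followed: 15.3% or 17.1%.
- One event in 20, exact (Clopper-Pearson) two-sided 95% interval: 0.1% to 24.9%.
- Chance of at least one event in an arm of 20 = 1 − (1 − p)^20. For true rates of 5%, 10% and 20%: 64%, 88% and 99%.
- Power of Fisher's exact test, two-sided 5%, for an illustrative 10% versus 30% with 20 per arm: 24%.

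The table would therefore describe common harms and could not support a test between arms.

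To illustrate reliance on spontaneous reports, assume a true rate of 20% in both arms (20 × 0.20 = 4 events each). If half were captured in both arms, the count would be 2 versus 2 and the rate would be understated by half. If half were captured in one arm only, it would be 4 versus 2, a 10-point difference from capture alone. The documents show neither pattern; the second is only a possibility.

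**The case against.** The strongest case against is that this is a 40-person feasibility pilot of an authorized digital program, its primary conclusions do not depend on event data, and even good capture would give wide intervals. All of that is true, and it limits the weight of the point. It does not remove it, because asking costs little and unasked events are lost.

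A reader might draw three stronger conclusions that the documents do not support.

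- **That harms could not be described by arm at all.** The repeated scales and actigraphy are scheduled identically in both arms, so some symptom worsening can be described. The gap concerns discrete events.
- **That the protocol promises to gather such data and fails to.** The commitment to pass on new information does not say it comes from this trial, and the withdrawal clause gives the study doctor discretion without committing to data collection. Weekly contact and the rule on ending a strained session can inform that discretion.
- **That the arms would be ascertained unequally.** The calls go to participants in both arms and the control is attention-matched. The absence of a script leaves unequal capture possible, not shown.

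Absence from the available text is also not proof of absence. The outline figure of visits, the consent pages and some other pages were not available, and a separate safety monitoring plan may exist.

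**Conclusion.** The point holds for discrete adverse events in the visible text: they are not systematically elicited, recorded or tabulated in either arm. It is worth correcting, because doing so changes what staff ask and what the trial can report. It is not critical, because the feasibility and acceptability conclusions stand without it.

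The loss is an approximate description of common harms: an upper bound near 14% if none were seen in an arm, assuming 1:1 allocation and full follow-up. Rare harms would stay out of reach either way. Confidence is medium, because material that was not available may already cover capture.

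**What to change.** 1. Add one scripted, open question about new or worsening health problems, falls, accidents and mood, worded identically for both arms, to the existing weekly contacts and to the week 9 and 24-week contacts. The 24-week question should cover the whole time since week 9.
2. Record every answer in REDCap, including none, and route serious reports to the study doctor.
3. Add one SAP table of participants with events by arm, with exact intervals and no hypothesis test.

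If a separate safety plan or a figure not shown already covers capture, cross-reference it and add only the table.

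**Cost.** Contacts per participant: 6 to 9 weekly calls plus two visits, so 8 to 11. At an assumed 1 minute each, 40 × 8 = 320 minutes (5.3 hours) to 40 × 11 = 440 minutes (7.3 hours). If the ninth call is also the week 9 contact, the upper figure is 40 × 10 = 400 minutes (6.7 hours). Recording and review, assuming 20 to 80 reports at 5 to 15 minutes each, adds 20 × 5 = 100 minutes (1.7 hours) to 80 × 15 = 1,200 minutes (20 hours). The total is about 7 to 27 hours, plus one form and one table. The assumed number and length of reports drive most of the upper figure.
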